**PHASE II: Multiple Baseline with Phase Change Procedures:** Participants (8) will be randomized to a 2- or 4-week initial baseline period. The baseline period will consist of assessment only, described in detail below. Following the initial baseline period, participants will receive 4 weekly 50-minute sessions of an intervention; this duration of treatment is consistent with clinical experience at our center indicating that this is an adequate amount of exposure to given UP modules. The Countering EDBs Module from the UP will be used as the basis for session content as the modular approach of the UP allows for the delivery of just this treatment topic isolation. Randomization to baseline phases of differing lengths will allow us to explore whether change on variables of interest occurs when and only when the intervention is applied. *Phase II Treatment Quality Assurance.* The PI (applicant) will serve as the study therapist. The PI is a licensed clinical psychologist with over eight years of experience with adults with BPD. Additionally, the PI is fully certified as an expert in the delivery of the UP. All therapy sessions will be audiotaped and will all be rated for adherence and competence ratings by an expert rater. Most importantly for the current project, integrity measures will assess for allowed and disallowed techniques within the UP to ensure only information regarding countering EDBs is presented as a means to isolate this putative mechanism. Descriptive statistics on fidelity measures will be obtained.

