*Phase II Assessment.* During all periods (baseline and intervention), participants will be asked to complete a daily log of EDBs and emotional intensity using SymTrend, a software developed specifically for real-time data collection. Participants will be trained in using their personal smart-phone to complete these daily logs on SymTrend. Participants who do not own a smart-phone will be excluded from this study; based on consultation with collaborator [name] who routinely conducts research using EMA and recent studies utilizing these methods at CARD, we anticipate very few participants will be excluded do to this criterion. Participants will be asked to self-initiate an entry whenever they are experiencing strong emotions (at least once per day) and will be asked to rate the intensity of their emotional experience. One hour after self-initiating the entry, participants will be prompted by text message via SymTrend to indicate whether they engaged in EDBs or acted inconsistent to emotional urges, as well as to rate their current emotional intensity. SymTrend will automatically send text messages everyday at mid-day to remind participants to self-initiate entries when feeling a strong emotion. Additionally, participants will receive a text-message reminder once a week prompting them to complete a longer self-report battery. Participants will have the option to complete the logs and questionnaire battery on a computer rather than smart phone, should they prefer. Phase II assessment measures will include: **Diagnostic Measures.** As in Phase I, the DIPD-IV and ADIS-5 (described above) will be used to confirm inclusion and exclusion criteria. **Major Assessment Measures.** Major assessments will be completed at four time-points: pre-baseline period, pre-intervention period, post-intervention, and post-follow up. These assessments will include: (1) Zanarini Rating Scale for Borderline Personality Disorder (ZAN-BPD). The ZAN-BPD is a continuous clinician-rated scale designed to address change in BPD symptoms by rating severity of the diagnostic criteria across a 1-week time frame. The ZAN-BPD has demonstrated high levels of reliability and validity. (2) Paced Auditory Serial Addition Task- Computerized Version (PASAT-C). The PASAT-C is behavioral measure that has been used with BPD participants as assess willingness to engage in goal-directed behavior while experiencing distress and will be used as a behavioral indicator of acting inconsistent with EDBs. **Weekly Measures.** As noted above, patients will be prompted to complete a self-report battery via text-message from SymTrend on a weekly basis. The battery will include the (1) self-report version of the ZAN-BPD (ZAN-BPD-srv) and the (2) Multidimensional Experiential Avoidance Questionnaire (MEAQ). The MEAQ is a self-report measure that will be used to assess emotional tolerance. The MEAQ has demonstrated high internal consistency and validity. Finally, (3) changes in medication will be tracked. **Daily Measures.** As described above, participants will be asked to self-initiate entries when experiencing a strong emotion. These entries will involve completing the PANAS-X and then, one hour later, completing a series of structured questions regarding engagement in EDBs, followed by an additional PANAS-X.

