**Participant Safety and Confidentiality: PHASES I & II.** The PI, working closely with her mentor, will carefully monitor the safety of participants. During Phase I, the PI will conduct a risk assessment following each study session to ensure that participants are safe to leave the laboratory after each emotion induction session. In the unlikely event that participants report increased risk, they will be encouraged to contact their existing treatment provider (Phase I does not preclude ongoing treatment) or will be given referrals if they do not have one. If risk is imminent, every measure will be taken to ensure participant safety (e.g., safety plan, hospitalization) in a manner consistent with customary clinical care at CARD. Because Phase II examines the effects of an intervention, participants will be asked to refrain from additional treatment during the baseline, treatment, and follow-up periods. It is important note that inclusion/exclusion criteria reflects the lower-risk BPD patients of interest in this study and these patients should be able to tolerate all periods of Phase II. Safeguards will be in place in the unlikely event that patients deteriorate. First, weekly questionnaire data will be examined as it is returned for indicators of clinical deterioration – email notifications will alert the PI to incoming data. Endorsement of increased suicidal ideation on the ZAN-BPD-srv (ratings of 2 or higher on item 5) will trigger a formal risk assessment; this will be conducted with 24 hours of receipt of the data. Issues of clinical deterioration and safety will be discussed during ongoing mentoring meetings with [name], who has also agreed to be available by cell for emergencies. Following long-standing customs of research studies at our Center, any patients deteriorating (as determined by a  $> 6$  point increase on the ZAN-BPD-srv) in any study phase will be brought to the attention of current clinical director of CARD, [name] (who is not

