*Phase II Data Analyses:* The multiple baseline and phase change design will make between- and within-subjects analysis possible. By applying different baseline lengths across individuals, between-series comparisons will be possible to determine if changes in EDBs, emotional intensity, and emotional tolerance occur when and only when the intervention is applied. The phase change (baseline phase to treatment phase) process will allow for within-series comparisons to examine concomitant changes in EDBs, emotional intensity, and emotional tolerance when treatment is present compared to when it is absent within individuals. For both between-and within-subjects comparisons, we will first plot parallel lines representing changes in these variables over time for each individual. These will be directly compared in terms of changes in level and slope to determine if differences seen are due to phase change. We will also conduct non-parametric randomization tests of mean differences in EDBs, emotional intensity, and emotional tolerance as a function of phase using the SCRT within the R statistical framework. Results from these tests will be used with visual inspection of data to draw conclusions regarding effects of the intervention on frequency of EDBs, emotional intensity and emotional tolerance. We will also explore maintenance effects of our intervention by examining stability in EDBs, emotional intensity, and emotional tolerance during the follow-up phase. Finally, as an exploratory analysis, we will examine phase effects (baseline, treatment, follow-up) on clinician rated and self-reported BPD symptoms.

*Phase II, Hypothesis I:* Individuals will demonstrate change in self-reported frequency of EDBs, intensity of emotion (PANAS) and tolerance of emotions (MEAQ), as well as behavioral willingness to act inconsistent with emotional urges (PASAT-C) only after treatment is applied. *Phase II, Hypothesis II:* Change in these variables will be maintained during a 4-week follow up period. *Phase II, Hypothesis III:* In this exploratory analysis, we hypothesize that clinician-rated and self-reported BPD symptoms (ZAN-BPD, ZAN-BPD-srv) will decrease when and only when the intervention is applied, and only for patients who demonstrate reduction in EDBs.

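### Nothing in Phase II keeps weekly MEAQ answers from the therapist, so a reporting shift that begins with therapy would be read as a phase effect

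*Combined protocol and SAP*

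**What the plan says.** All locations are in the combined protocol and SAP, under Research Design.

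- **Therapist.** Phase II Treatment Quality Assurance: "The PI (applicant) will serve as the study therapist". No second therapist is named. All sessions are audiotaped and rated, with checks on allowed and disallowed techniques.
- **Flow of weekly data.** Participant Safety and Confidentiality: "weekly questionnaire data will be examined as it is returned for indicators of clinical deterioration", and "email notifications will alert the PI to incoming data". The two numeric triggers in that section, one on item 5 and one on the change in score, both use the ZAN-BPD-srv.
- **Contents of the battery.** Phase II Assessment: "The battery will include the (1) self-report version of the ZAN-BPD (ZAN-BPD-srv) and the (2) Multidimensional Experiential Avoidance Questionnaire". Medication changes are tracked in the same battery. On its role: "The MEAQ is a self-report measure that will be used to assess emotional tolerance".
- **Use in the analysis.** Phase II, Hypothesis I names the MEAQ as the tolerance measure. Phase II Data Analyses: "We will also conduct non-parametric randomization tests of mean differences in EDBs, emotional intensity, and emotional tolerance as a function of phase", read together with visual inspection.
- **Design.** "Participants (8) will be randomized to a 2- or 4-week initial baseline period", then four weekly sessions and a four-week follow-up.

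Phase II Assessment Quality Assurance discusses bias only for the independent evaluators, and does not require them to be blind. No section limits who sees MEAQ answers, gives them to a reader other than the PI, or tells participants who will see them.

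**The concern.** The person who delivers the therapy is also the one named recipient of alerts about a self-report outcome of that therapy. No stated safety trigger needs that outcome. Two routes to bias are open. A participant may report more progress once in a therapy relationship with someone who can see the answers. The therapist, seeing MEAQ scores, may steer sessions toward its content without intending to.

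Either effect would begin around the first session. Randomized baseline lengths protect against calendar trends and the effects of repeated assessment, because those do not follow the individual's start date. They do not protect against something that does follow it. The plan would then show the pattern Hypothesis I predicts for tolerance without any real change in tolerance.

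**Working it through.** **1. The plan's own counts.** With a 4:4 split (assumed; the plan does not state it), participant-weeks = 4 × (2+4+4) + 4 × (4+4+4) = 40 + 48 = 88, and 88 × 7 = 616. Both match Power Analyses. The 88 weekly batteries divide into 24 in baseline (4×2 + 4×4), 32 in treatment and 32 in follow-up. The alert to the PI applies to all of them.

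**2. What the contrast removes and keeps.** For each participant, d = mean(treatment weeks) − mean(baseline weeks).

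- A shift c present in every week: (T + c) − (B + c) = T − B, so it cancels.
- A shift b present only from the start of treatment: (T + b) − B = (T − B) + b, so it passes in full into d, whichever baseline length was drawn.

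**3. Effect on the planned type of test.** Assumptions: no true effect, independent weekly values with within-person SD 1, a 4:4 split, and a shift in the hypothesized direction. The test statistic is the mean of d over eight participants. Its reference set is the C(8,4) = 70 ways to assign the two baseline lengths, and the test is one-sided at 5%. The plan gives no alpha, sidedness or exact statistic, so these choices are illustrative. The attainable level is 3/70 = 4.3%. Each row comes from 40,000 simulated trials.

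| Shift b (SD) | Mean phase difference | Rejection rate |
|---|---|---|
| 0 | 0.00 | 4.3% |
| 0.1 | 0.10 | 5.8% |
| 0.2 | 0.20 | 7.7% |
| 0.3 | 0.30 | 9.9% |
| 0.5 | 0.50 | 15.5% |
| 1.0, all weeks including baseline | 0.00 | 4.3% |

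With lag-1 autocorrelation of 0.3, a smaller simulation (1,500 trials) gave about 9% at b = 0.25 and 16% at b = 0.5, so the picture does not depend on independence.

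**4. Why rejection rises slowly while the estimate moves in full.** A participant analyzed under the wrong baseline length still shows half the shift. If the true baseline is 2 weeks and it is analyzed as 4, two of the four supposed baseline weeks carry b, so d = b − b/2 = b/2. If the true baseline is 4 and it is analyzed as 2, two of the four supposed treatment weeks carry b, so d = b/2 − 0 = b/2. The reference distribution therefore moves with the data and damps the test. The estimate and the plotted series, which visual inspection reads, are not damped.

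**The case against.** The strongest reply is that access does not change at the phase boundary. Weekly data reach the PI in baseline too, and under Participant Retention the PI meets each participant at the baseline assessment, with the stated aim of building an alliance with the research team. A wish to please the PI may already be present in baseline and would cancel. This stands. It limits the concern to whatever the therapy relationship adds, and some of that would arise whoever read the MEAQ.

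The safety section also says in the passive that the data are examined. It does not say that the PI reads MEAQ items or uses them in sessions, or that participants know who reads them. A reader might infer that the therapist coaches on the MEAQ, or that participants answer knowing the therapist will look. The documents support neither; they only leave both open.

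Two safeguards exist, and each is partial. The integrity ratings could catch overt coaching, but they are not described as checking for discussion of questionnaire answers, and they cannot detect answering to please. The PASAT-C is behavioral, but it is given only at the four major assessments and indexes acting inconsistent with emotion-driven behaviors, not MEAQ tolerance.

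A reader might also take larger rejection rates from a normal-theory test. There the variance of the mean difference is [4(1/2+1/4) + 4(1/4+1/4)]/64 = 0.0781, so SE = 0.28, and one-sided rejection is 10%, 18% and 28% at 0.1, 0.2 and 0.3 SD. The plan specifies randomization tests, which inflate much less, so those figures should not be used.

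**Conclusion.** The point holds as an avoidable risk to one Hypothesis I outcome, emotional tolerance measured by the MEAQ. The chain is in the documents: a single therapist, alerted to incoming weekly data that include a tested self-report outcome, with no separation described. Any part of a reporting shift that starts with therapy is indistinguishable from a treatment effect of the same size under this design. The illustrative cost is the full shift in the estimate, with false-positive rates of about 6% to 16% for shifts of 0.1 to 0.5 SD. This rests on a 4:4 split, independent weekly values and a one-sided 5% test. The documents give no basis for choosing a value within that range.

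It does not show that the Phase II results will be biased. Nor does it extend to the daily PANAS-X and behavior logs: a reader might assume the therapist sees those as well, but the alert is described for weekly questionnaire data only.

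**What to change.** In Phase II Assessment Quality Assurance and in Participant Safety and Confidentiality:

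1. State that MEAQ responses are withheld from the PI as therapist until that participant has completed follow-up. If the team regards the MEAQ as part of its review for deterioration, name someone who does not deliver the therapy to read it.
2. Tell participants at pre-baseline that their therapist will not see their MEAQ answers. Without this, withholding addresses steering in sessions but not answering to please.
3. Leave the ZAN-BPD-srv, medication tracking, and the existing safety review, triggers and timing unchanged.
4. In the report, state that the ZAN-BPD-srv was visible to the therapist, and that some self-report bias from open treatment remains.

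No restriction on the daily logs is needed on this ground.

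The cost is one access rule and one sentence to participants, assuming the data system can restrict access by measure, which the documents do not say. The therapist loses sight of MEAQ scores during treatment. The change has to be made before Phase II data collection, because the exposure cannot be undone afterwards.

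### Phase II emotional intensity and EDB frequency are recorded only through entries participants start when emotion is strong (minimum one a day), so phase means also reflect which moments are reported and how often

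*Combined protocol and SAP*

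**What the plan says.** All references are to the Combined protocol and SAP.

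Phase II Assessment sets the trigger for the daily log: "Participants will be asked to self-initiate an entry whenever they are experiencing strong emotions (at least once per day". The EDB question follows from that entry: "One hour after self-initiating the entry, participants will be prompted by text message via SymTrend to indicate whether they engaged in EDBs". The daily measures are described the same way: "These entries will involve completing the PANAS-X and then, one hour later, completing a series of structured questions regarding engagement in EDBs", after which a second PANAS-X is completed. The only scheduled daily contact is a reminder: "SymTrend will automatically send text messages everyday at mid-day to remind participants to self-initiate entries when feeling a strong emotion".

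No other instrument records daily intensity or EDB frequency. The MEAQ (weekly) covers emotional tolerance and the ZAN-BPD covers BPD symptoms. The PASAT-C, given at four assessments, "will be used as a behavioral indicator of acting inconsistent with EDBs".

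Phase II, Hypothesis I reads: "Individuals will demonstrate change in self-reported frequency of EDBs, intensity of emotion (PANAS) and tolerance of emotions (MEAQ", together with PASAT-C performance, with change expected only once treatment is applied. The Phase II analysis states: "We will also conduct non-parametric randomization tests of mean differences in EDBs, emotional intensity, and emotional tolerance as a function of phase". It does not say whether EDBs are a count per day or a share of entries, how several entries in one day are combined, or how a change in entry rate is handled.

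The safeguards are the once-a-day minimum, the reminder, and a $100 bonus for at least 80% compliance. No denominator is given for compliance with entries that participants start themselves.

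**The concern.** Intensity is rated at moments chosen because intensity is high, so the outcome helps select its own observations. If treatment lowers emotion, fewer moments qualify as strong, and those that remain are a different selection. The once-a-day rule then adds obliged entries from calmer days, and their share of all entries can itself change with treatment. The mean over entries therefore need not follow the mean of the person's emotion.

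EDBs are asked about only after an entry, so the recorded count is the number of entries multiplied by the chance of acting on the urge. A change in either factor moves the count. The module teaches people to counter emotion-driven urges, so it could plausibly alter how readily they notice or report them.

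At stake is the central inference of a multiple-baseline design, that change appears at the intervention and not before. Baselines of 2 and 4 weeks help against drift in reporting over calendar time. They do not help if reporting shifts when treatment starts, because that shift is staggered in the same way as the treatment.

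**Working it through.** **1. The plan's own count.** Power Analyses gives 88 weekly and 616 daily observations. Baseline is 2 or 4 weeks, intervention 4 and follow-up 4. Assuming the 8 participants split 4/4 (not stated), 4 × (2+4+4) + 4 × (4+4+4) = 40 + 48 = 88 person-weeks, and 88 × 7 = 616 person-days. Both figures reproduce. So 616 means one value per person per day at full compliance, although the log is event-driven and the rule for reducing a day to one value is not given. The total includes follow-up, whereas the log is described thus: "During all periods (baseline and intervention), participants will be asked to complete a daily log of EDBs and emotional intensity using SymTrend". Without follow-up it would be 4 × (2+4) + 4 × (4+4) = 56 person-weeks, or 392 days.

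**2. Intensity, with emotion truly lower.** The documents give no SD, entry rate or definition of strong, so these inputs are assumptions: momentary intensity with SD 1 and first-order autoregressive correlation within the day (0.3 or 0.7); 5 or 10 waking occasions a day; strong defined as above 0.5, 1.0 or 1.5 SD; true fall 0.5 SD. That makes 2 × 2 × 3 = 12 settings, each simulated over 40,000 days. Share of effect shown = (mean of all entries before − mean after) / 0.5.

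| Entry rule | Share of the true fall shown |
|---|---|
| Once a day; obliged entry is the day's strongest moment | 78–117% in 10 of 12 settings; about 42% and 55% in the other two |
| Once a day; obliged entry is a random moment | about 67% to 208%, mostly above 100% |

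Across both versions of the rule the range is roughly 43% to 208%; the ends move by a few points between simulation runs. Entries per day fall by 5–42%.

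**3. Intensity, with no true change but altered reporting.** Let intensity be N(0,1), with entries made only above a threshold c. The minimum is left out here, so this shows direction only. Mean of entries = φ(c) / [1 − Φ(c)]; share of moments reported = 1 − Φ(c).

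- c = 0: mean 0.798, reported 0.500
- c = 0.5: mean 1.141, reported 0.309
- c = 1.0: mean 1.525, reported 0.159

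If participants begin to report milder moments (0.5 to 0), the mean falls by 1.141 − 0.798 = 0.34 SD and the EDB count is multiplied by 0.500/0.309 = 1.62 at a constant chance of acting. If they report fewer (0.5 to 1.0), the mean rises by 0.38 SD and the count is multiplied by 0.159/0.309 = 0.51. Nothing in the person's emotion has changed in either case.

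**4. EDB count.** Observed reduction = 1 − (1 − true reduction) × (reporting probability after / before). The probabilities are assumed.

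- 0.8 to 0.6, no true change: 1 − 0.75 = 25% apparent fall.
- 0.8 to 0.6, true 30% fall: 1 − 0.7 × 0.75 = 47.5%.
- 0.6 to 0.8, no true change: 1 − 1.333 = a 33% apparent rise.
- 0.6 to 0.8, true 30% fall: 1 − 0.7 × 1.333 = 7%.

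**5. EDB share of entries.** Take one entry a day, with an EDB probability of 0.6 after strong and 0.2 after weak emotion (assumed). If strong-emotion entries go from 90% to 60%, the share goes from 0.9 × 0.6 + 0.1 × 0.2 = 0.56 to 0.6 × 0.6 + 0.4 × 0.2 = 0.44, with no change in the response to strong emotion. Moving from count to share does not remove the selection.

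**The case against.** Event-triggered logging suits the question. The theory concerns the intensity of an activating emotion and what the person does next, and the paired PANAS-X ratings an hour apart parallel the Phase I comparison of post-induction with post-regulation intensity. A fixed midday rating measures something else. This stands, and is why such a rating should be added rather than substituted.

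A reader might infer that the design hides a real effect almost completely. With entries only above the threshold and no daily minimum, the same simulation shows just 13–24% of a 0.5 SD fall. The plan requires at least one entry a day, so that figure describes a design it does not use. With the rule, many settings come near or above 100%.

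A reader might also take every fall in entries or EDBs as an artefact. Fewer strong episodes, and so fewer EDBs, is a genuine fall in frequency. In step 2 entries drop because emotion was truly lowered.

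Much of the intensity problem also depends on an unspecified summary. If the obliged entry is the day's strongest moment and each day is summarised by its highest entry, the simulated effect is recovered in full in all 12 settings. With a random obliged entry, the same summary overstates it (122–183%). So an instruction and an aggregation rule could do part of the work, but neither is in the plan, and neither deals with a reporting change at treatment onset.

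Finally, the minimum, the reminder and the bonus limit silent days. They do so by mixing obliged and strong-emotion entries in proportions that treatment can change.

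**Conclusion.** The concern holds for two of the four Hypothesis I outcomes, PANAS-X intensity and EDB frequency. As collected, a phase difference in either mixes change in emotion or behaviour with change in which moments are reported. The error can go either way. The 43–208% range rests wholly on the assumed inputs and on pooling all entries; the documents supply neither, and they give no basis for the size of any reporting change. What follows from the documents is the dependence itself, and the inability of staggered baselines to remove a reporting shift that begins with treatment.

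It would go too far to call these the main Phase II outcomes. Hypothesis I does not rank its four, although Phase II Assessment Quality Assurance does put the primary focus on changing EDBs. Nor is Phase II as a whole undermined, since the MEAQ and PASAT-C do not depend on entry rate. This is an inexpensive improvement, best made before Phase II data collection, because an unselected series cannot be recovered by later analysis.

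**What to change.** 1. Keep the midday reminder, and have the same text collect a brief PANAS-X rating of current emotion, answered whatever its strength. Analyse that series by phase as the unselected measure of intensity, beside the event-triggered ratings and their one-hour change. Run it in every phase to be compared, including follow-up if Hypothesis II is to use it.
2. Add to that prompt an EDB question covering the time since the previous prompt. Otherwise, state that EDB frequency is conditional on self-initiated entries.
3. Report by phase the entries per day, the EDB count per day and the EDB share of completed one-hour prompts. Claim an EDB effect only when it is not explained by a change in entry rate. If count and entry rate fall together while the share is steady, the self-initiated log alone cannot tell fewer episodes from less reporting; the midday series can help.
4. Flag once-a-day entries made without strong emotion, and fix in advance how several entries in a day are combined and how days without an entry are treated.

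The cost is one extra short rating a day on a text already sent, slightly more participant burden, and some analysis wording. Treatment, visits and sample size are unchanged. The midday EDB question is still self-report, so it removes the dependence on opening an entry but not every effect of greater awareness.
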